The ADAPT-Sepsis is a multi-centre three-arm randomised controlled trial with internal pilot. Participants are randomly allocated using a ratio 1:1:1 to CRP: PCT: Usual care. A computerised minimisation randomisation system was used, created by the Warwick Clinical Trials unit, to randomise participants. The randomisation allocation was made following consent processes and baseline assessments. Stratification factors were (i) sepsis severity (sepsis or septic shock), (ii) recruitment centre and (iii) surgery within the last 72 hours or not.

Primary and secondary outcomes

The primary outcomes are effectiveness outcome of total duration of antibiotics used to 28 days post randomisation and safety outcome of 28 days all-cause mortality. Secondary outcomes include escalation of care/re-admission; infection re-lapse/recurrence; dose of antibiotics; length and level of critical care stay, length of hospital stay, and 90-days all-cause mortality.

Sample size

A total sample size of 2760 would be able to detect both a mean of 1-day reduction in antibiotic use duration (using a mean antibiotic duration of 7 days, a pooled standard deviation of 6 days, 90% power, a significance level of 5%, with a 5% withdrawals rate) and a non-inferiority safety margin of 5.4 % (using a 1-sided significance level of 2.5%, 90% power and 5% withdrawal rate) assuming 28-day mortality is 15%.

Timing of final analysis

The end of the trial is defined when the last recruited participant completed 28-days follow-up post randomisation. Once all the data have been entered onto the database, the data will be fully validated and cleaned after which the database will be locked, and the final analyses will be undertaken.

Timing of outcome assessments

Primary and secondary outcome data will be collected daily from randomisation until hospital discharge. Data will also be collected post hospital discharge up to 28-days post randomisation. All-cause mortality

will be collected at 90 days using linked data. Any SAE's will also be reported up to 28 days post-randomisation.

Reporting of results

All primary and secondary clinical effectiveness outcomes will be reported in an earlier publication, with process of care and health economics outcomes reported in subsequent publications, when all the data are available.

In addition, the sub-study, RISC-sepsis will also be reported in a further publication (and has its own approved statistical analysis plan).

Statistical principles

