- Number of randomised patients included in the final analyses at the primary endpoint(s)

Withdrawal and follow-up

Participants may be discontinued from the trial at any time. They can either withdraw from the intervention alone but remain on follow-up or they can withdraw completely from the trial. Unless a participant explicitly withdraws their consent, they will be followed-up wherever possible and data collected as per the protocol until the end of the trial. The number of withdrawals from the trial will be summarised by treatment arms, that is, how many participants withdrew from intervention alone but remained on follow-up and how many withdrew completely from the trial. In addition, the withdrawal timings will also be summarised by treatment arms. It will include withdrawals after randomisation but before hospital discharge, and withdrawals after hospital discharge but before 28 days follow-up. The withdrawal decision i.e. decision made by the participant, consultant, clinical team, antibiotic stopped due to futility, required >21 days of antibiotics post randomisation and

other, will be summarised by treatment arms. Follow-up rates will be computed at the 28-day and 90-day follow-up time-points. At 90 days, only all-cause mortality data will be collected using NHS digital and the Intensive Care National Audit and Research Centre.

Baseline patient characteristics

The baseline demographic characteristics and pre-randomisation clinical measures of all randomised participants will be summarised by treatment arms. Moreover, important process data (e.g. date and time of hospital admission and ICU/HDU admission) will also be collected and summarised by treatment arms. Continuous data will be summarised using the statistics the number of participants (n), mean, standard deviation (sd), median and interquartile range (IQR) whereas categorical data will be summarised using the statistic the number (%) of participants. The table below lists the demographic, clinical measures and process variable data that will be collected and summarised.

- Age
- Gender
- Suspected septic shock
- Surgery within last 72 hours
- Core body temperature
- White cell count
- Critical care admission category
- Critical care origin
- Initial care bundle
- qSOFA score
- SOFA score
- APACHE II score
- Infection data:
 - Community/hospital acquired infection
 - Site of infection
 - Causative microorganism identified for infection
 - If yes to the above, detail pathogen

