The primary effectiveness analyses will assess whether any of the biomarker interventions are better than standard care. The primary analysis approach for the duration of antibiotics will be intention-to-treat (ITT). ITT analysis will consist of all randomised patients and will assess the effect of treatment assignment. For the ITT analysis, linear mixed effects regression models will be fitted to estimate the treatment effect having adjusted for age, gender and the stratification variables (sepsis severity, recruiting centre (random effect) and surgery within the last 72 hours). After fitting the model, we will investigate the validity of the assumption of normality. Alternative methods of analyses will be considered if the distribution of the primary effectiveness outcome is non-normal. In this trial, participants may die before antibiotic therapy is discontinued. In such cases the outcome is undefined and is referred to as 'truncated by death'. A crude comparison between the survivors on each treatment arm may give rise to biased outcome comparisons. Therefore, we will consider undertaking some sensitivity analyses to estimate treatment effect having account for the deaths. This will explore different approaches to analysis of ICU trials, that allow incorporation of multiple relevant outcomes, including death, into a single overall measure (e.g., the win ratio⁸, global ranking score⁹, and weighted composite outcome¹⁰).

The primary safety outcome (28-day all-cause mortality) is based on assessing non-inferiority and we specify the null hypothesis that the biomarker interventions are much worse compared with standard-of-care. The primary safety outcome will be analysed using mixed effect logistic regression models, using the same adjustments variables as the primary effectiveness analysis. We will derive risk difference from the fitted logistic regression model to compare the non-inferiority margin for the safety outcome. The unadjusted and adjusted estimates and the 95% confidence intervals will be compared with the non-inferiority margin to accept/reject the null hypothesis. Therefore, our primary effectiveness outcome (antibiotic duration) will not provide all the information as regards the treatment effect. Safety (28-day all-cause mortality) is paramount - only if an intervention arm is not worse than the control (standard care only) will it be acceptable.

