Secondary outcomes will be assessed using an ITT approach. Continuous secondary outcomes will be analysed in the same way to the primary outcome and the categorical outcomes will be assessed using mixed effects logistic regression models. Time-to-event outcomes will be analysed using Cox

proportional hazards models. For all analyses, the adjusted effect estimates will be presented along with their associated 95% confidence interval (CI). In addition, the primary outcomes will also be analysed using Bayesian method as secondary analysis considering both non-informative and informative priors.

Exploratory sub-group analyses for primary effectiveness outcome will be reported using 99% confidence intervals. Linear mixed effect regression will be used with interaction terms (treatment group by sub-group) to estimate sub-group effects. The following sub-groups selected from a recent report about the management of infection causing sepsis in the NHS will be explored:

- Community-acquired pneumonia (CAP)
- Hospital-acquired pneumonia (HAP)
- Urinary tract infection (UTI)
- Intra-abdominal infection
- Infection with positive blood culture

In addition, community acquired, hospital acquired infections and SARS-COV-2 will be analysed as subgroup. Moreover, we will do the following subgroups analysis

- Sepsis vs Septic Shock
- Ward vs ICU where the intervention was stopped
- Surgery vs non-surgery on previous 72 hours

An exploratory analysis will be done to investigate weekend effect on the primary effectiveness outcome, the total duration of antibiotic treatment to 28 days from randomisation. Monitoring of the protocol processes and compliance measures is important in this trial (as detailed in section 4). These measures will be monitored and reported to the DMC throughout the trial. A final summary of the protocol processes and compliance will be presented at the end of the trial.

Handling missing data

Every effort will be made to minimise missing data both in baseline and outcome in the trial. Missing data will be assessed carefully. For the primary outcome (duration of antibiotics), start and stop dates for each course of antibiotics are required in order to compute the total duration for each participant. There will be no missing for start dates as the start dates and times will be the

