Emergency surgical	n (%)	n (%)	n (%)	n (%)
Other	n (%)	n (%)	n (%)	n (%)
Missing	n (%)	n (%)	n (%)	n (%)
Origin				
Emergency department	n (%)	n (%)	n (%)	n (%)
Emergency admissions unit	n (%)	n (%)	n (%)	n (%)
Medical ward	n (%)	n (%)	n (%)	n (%)
Surgical ward	n (%)	n (%)	n (%)	n (%)
Another critical care unit	n (%)	n (%)	n (%)	n (%)
Other	n (%)	n (%)	n (%)	n (%)
Missing	n (%)	n (%)	n (%)	n (%)
Core body temperature (°C)				
N	n (%)	n (%)	n (%)	n (%)
Mean (SD)	n (%)	n (%)	n (%)	n (%)
Median (IQR)	n (%)	n (%)	n (%)	n (%)
Missing	n (%)	n (%)	n (%)	n (%)
White cell count (x10⁹/L)				
N	xx.xx	xx.xx	xx.xx	xx.xx
Mean (SD)	xx.xx	xx.xx	xx.xx	xx.xx
Median (IQR)	xx.xx	xx.xx	xx.xx	xx.xx
Missing	xx.xx	xx.xx	xx.xx	xx.xx
Infection acquirement				
Community acquired	n (%)	n (%)	n (%)	n (%)
Hospital acquired	n (%)	n (%)	n (%)	n (%)
Missing	n (%)	n (%)	n (%)	n (%)

Site of infection causing sepsis*				
Respiratory tract	n (%)	n (%)	n (%)	n (%)
If yes above, was it pneumonia	n (%)	n (%)	n (%)	n (%)
If yes above (pneumonia), was it ventilator related	n (%)	n (%)	n (%)	n (%)
Central nervous system	n (%)	n (%)	n (%)	n (%)
Skin and soft tissue	n (%)	n (%)	n (%)	n (%)
Is yes above, was it a surgical site infection	n (%)	n (%)	n (%)	n (%)
Central line related infection	n (%)	n (%)	n (%)	n (%)
Intra-abdominal	n (%)	n (%)	n (%)	n (%)
Urinary tract	n (%)	n (%)	n (%)	n (%)
If yes above, was it associated with a urinary catheter	n (%)	n (%)	n (%)	n (%)
Ear, nose and throat	n (%)	n (%)	n (%)	n (%)
Blood stream	n (%)	n (%)	n (%)	n (%)
If yes above, was it primary	n (%)	n (%)	n (%)	n (%)
Unknown focus	n (%)	n (%)	n (%)	n (%)
Other	n (%)	n (%)	n (%)	n (%)
Is there a causative microorganism identified for the infection causing sepsis				
No	n (%)	n (%)	n (%)	n (%)
Yes	n (%)	n (%)	n (%)	n (%)
Missing	n (%)	n (%)	n (%)	n (%)
Pathogens				
	n (%)	n (%)	n (%)	n (%)
	n (%)	n (%)	n (%)	n (%)

* Each site of infection is summarised separately for all participants. Therefore, it is possible that participants report more than one presumed site of infection causing sepsis.

Table 5: Initial care bundle at baseline summarised by treatment arm

	Standard care	PCT	CRP	TOTAL
Within 3 hours of presentation				
Was lactate level measured				

	No	n (%)	n (%)	n (%)	n (%)
	Yes	n (%)	n (%)	n (%)	n (%)
	Missing	n (%)	n (%)	n (%)	n (%)
Were blood cultures obtained prior to first antibiotics					
	No	n (%)	n (%)	n (%)	n (%)
	Yes	n (%)	n (%)	n (%)	n (%)
	Missing	n (%)	n (%)	n (%)	n (%)

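### The primary duration model is valid, but adding infection site and community/hospital acquisition could give a modest gain in precision whose size the SAP does not let us fix

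*SAP*

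**What the plan says.** Under Analysis methods, the duration outcome is analysed by intention to treat with a linear mixed model "adjusted for age, gender and the stratification variables (sepsis severity, recruiting centre (random effect) and surgery within the last 72 hours". This covers all three stratification factors named under Trial design, and adds age and gender. The mortality model is then given the same covariates as the duration model.

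Under Baseline patient characteristics, the infection data to be collected include "Community/hospital acquired infection" and "Site of infection". Template Table 4 lists the sites one by one, with rows for unknown focus and other, and notes that "it is possible that participants report more than one presumed site of infection causing sepsis". Its acquisition item has a row for missing values.

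The same infection features return in the exploratory subgroup analyses of duration: "The following sub-groups selected from a recent report about the management of infection causing sepsis in the NHS will be explored", followed by community-acquired pneumonia, hospital-acquired pneumonia, urinary tract infection, intra-abdominal infection and positive blood culture. The SAP adds that "community acquired, hospital acquired infections and SARS-COV-2 will be analysed as subgroup". These are examined as treatment-by-subgroup interactions in linear mixed models.

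**The concern.** The outcome is how long antibiotics are given, and infection type is a natural candidate predictor of it. The SAP already goes beyond the stratification factors by adding age and gender, so it accepts adjustment for baseline covariates. It does not say why infection type is left out. If site and acquisition do predict duration, their variance stays in the residual and the interval around the treatment difference is wider than it needs to be. What is at stake is some precision on the effectiveness outcome. The validity of the comparison is not in question.

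**Working it through.** **Inputs from the SAP** (Sample size; Confidence intervals and p-values; Trial design): "A total sample size of 2760 would be able to detect both a mean of 1-day reduction in antibiotic use duration", with SD 6 days, 90% power, 5% withdrawals, two-sided 5% and 1:1:1 allocation.

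**The plan's own figure.** The duration inputs alone give n per arm = 2 × 6² × (1.960 + 1.282)² / 1² = 757. Dividing by 0.95 gives 797 per arm, or 2391 in total. The plan's 2760 also has to serve the non-inferiority outcome, so it more than covers the duration target. How 2760 was reached is a separate matter.

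**Power and precision as planned.**
- Evaluable per arm: 2760 / 3 × 0.95 = 874
- Standard error: 6 × √(2/874) = 0.287 day
- 95% half-width: 1.96 × 0.287 = 0.563 day
- Power for 1 day: Φ(1/0.287 − 1.96) = 93.6%

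**With the infection covariates added.** The SAP gives no share of variance explained, so it is an assumption here. Let R² be the share explained beyond the present covariates. The residual SD becomes 6 × √(1 − R²). The last column is 2622 × (1/(1 − R²) − 1), where 2622 = 3 × 874.

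| Assumed extra R² | Residual SD (days) | 95% half-width (days) | Power, two-sided 5% | Equivalent extra evaluable patients, three arms |
|---|---|---|---|---|
| 0% | 6.000 | 0.563 | 93.6% | 0 |
| 1% | 5.970 | 0.560 | 93.8% | 26 |
| 3% | 5.909 | 0.554 | 94.3% | 81 |
| 5% | 5.848 | 0.548 | 94.7% | 138 |
| 10% | 5.692 | 0.534 | 95.7% | 291 |

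**What such R² values would require.** A binary covariate with prevalence p and a difference of d days in mean duration explains p(1 − p)d²/36 of the variance. For d = 2 this is 1.0% at p = 10% and 2.8% at p = 50%. For d = 3 it is 2.3% and 6.3%. A single feature of moderate effect therefore sits in the lower part of the range, and 10% would need several features or large differences.

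The calculation takes 6 days as the residual SD under the present covariates. Site and acquisition may overlap with surgery, septic shock and centre, which are already in the model. Only what they explain beyond those counts.

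**The case against.** The strongest reply is that nothing here is wrong. The covariates are fixed explicitly, they include every stratification factor, and the SAP nowhere promises to adjust for infection type. The effectiveness outcome exceeds its 90% power target without the extra terms. Across the assumed range the half-width shrinks by 0.003 to 0.029 day, about 4 to 42 minutes, against a target difference of 1 day. All of this stands, and it is why the point is an optional improvement.

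Three stronger readings are tempting, and the document supports none of them.

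- A reader might infer from the subgroup list that the SAP itself treats these variables as prognostic. It does not. The site subgroups are "selected from a recent report about the management of infection causing sepsis in the NHS will be explored", and they are tested as interactions. That concerns whether the treatment effect differs, which is a different question from how strongly infection type predicts duration.
- A reader might infer that power is short of 90% and that adjustment would restore it. That requires testing each biomarker comparison at 2.5%, where power is 89.3% without the new terms. The SAP tests at two-sided 5% and adopts no such split.
- A reader might infer that chance imbalance in infection type is a further problem, because it is not a minimisation factor. Such imbalance is random error that the confidence interval already reflects. Counting it again would count the same variance twice.

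It is also fair to say that the change is not free. Sites overlap, acquisition can be missing, and Handling missing data gives no rule for missing model covariates. As the text stands, new terms would also pass into the mortality model.

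**Conclusion.** The point holds as a modest efficiency improvement. The present model is valid, unbiased under randomisation and adequately powered at the SAP's own significance level. Adjusting for site and acquisition would narrow the 95% interval by about 0.5% to 5% and add 0.2 to 2.0 percentage points of power (unrounded, 93.63% to 93.84% or 95.66%). This rests on an assumed extra 1-10% of variance explained, SD 6 days and 874 evaluable patients per arm. At zero extra variance explained, the gain is zero. The case for acting is that the data are already collected and much of the coding is needed anyway for the planned subgroup models.

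**What to change.** Before unblinding, amend the duration model as follows.

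- Add baseline indicators for respiratory, intra-abdominal, urinary and other/unknown site, with the remaining Table 4 sites mapped to the last group. Let the indicators overlap, because a participant may have more than one site.
- Add community versus hospital acquisition, with a separate category for missing, so that no randomised patient is dropped for a missing covariate.
- Keep the present covariate set as a named sensitivity analysis.
- Amend the sentence that gives the mortality model the same covariates, so that the non-inferiority analysis keeps its present set unless an extension is separately prespecified. Continuous secondary outcomes are to be analysed like the primary outcome, so say which set they use.

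The cost is a few extra model terms, a written coding and missing-covariate rule, and two changed sentences (plus a clause for the continuous secondary outcomes). No new data are needed. If the sponsor prefers the present model, a line recording why infection type is left out would close the point.

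### The 28-day mortality model omits the baseline APACHE II and SOFA scores: a valid choice, but one that gives up a modest amount of precision on the non-inferiority endpoint

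*SAP*

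**What the plan says.** Under Analysis methods, the SAP carries the covariate set over from one co-primary outcome to the other: "The primary safety outcome will be analysed using mixed effect logistic regression models, using the same adjustments variables as the primary effectiveness analysis". The effectiveness model that this points to is "adjusted for age, gender and the stratification variables (sepsis severity, recruiting centre (random effect) and surgery within the last 72 hours". Severity therefore enters as a two-level factor, sepsis or septic shock, which is also one of the factors balanced at randomisation (Trial design).

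The list under Baseline patient characteristics includes "APACHE II score" and the SOFA score. That section introduces its content as demographic data and pre-randomisation clinical measures. Template Table 6 summarises both scores by arm and has a row for missing values under each. Neither score appears in a primary model.

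Analysis methods also says that a risk difference will be derived from the logistic model, and that both the unadjusted and the adjusted estimates, with their 95% intervals, will be held against the non-inferiority margin. It does not say which of the two decides.

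**The concern.** The covariates were chosen with antibiotic duration in view and reused for death without a stated reason. For death, a graded score of acute illness taken before randomisation can be expected to carry information beyond a two-level severity factor plus age. A prespecified prognostic covariate reduces the variance of the standardised risk difference. It also corrects for chance imbalance in severity within the two strata, which minimisation on sepsis versus septic shock does not control.

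This is the endpoint on which precision matters most. The SAP calls safety paramount and accepts an intervention arm only if it is not worse than standard care. The sample size leaves no slack here, as shown below. At stake is a somewhat wider interval than the collected data could give, and with it a slightly higher chance that a truly non-inferior arm fails to show it.

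**Working it through.** **Inputs from the SAP (Sample size and Trial design).** "A total sample size of 2760 would be able to detect both a mean of 1-day reduction in antibiotic use duration"; "a non-inferiority safety margin of 5.4" percentage points; "using a 1-sided significance level of 2.5%, 90% power and 5% withdrawal rate"; "assuming 28-day mortality is 15" per cent. Allocation: "Participants are randomly allocated using a ratio 1:1:1 to CRP: PCT: Usual care". Mortality is taken as equal in the arms compared. The normal quantiles are 1.96 and 1.2816.

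**Step 1: the plan's own figure.** The unpooled normal approximation for one comparison with control is

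n per arm = 2 × p(1 − p) × (1.96 + 1.2816)² / margin² = 2 × 0.1275 × 10.51 / 0.054² ≈ 919.

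Three arms give 2757, which matches 2760 before any withdrawal. With 5% withdrawal, 919 / 0.95 rounds up to 968 per arm, or 2904 in total. For mortality, then, 2760 does not contain the stated allowance. The evaluable number is 920 × 0.95 = 874 per arm.

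**Step 2: power without covariates at 874 per arm.** SE = √(2 × 0.1275 / 874) = 0.01708. Power = Φ(0.054 / 0.01708 − 1.96) = 88.5%, against 90.0% at 920 per arm.

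**Step 3: power with covariates.** If baseline covariates explain a share R² of the outcome variance, the variance of the marginal risk difference is multiplied by about (1 − R²), so

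Power = Φ(0.054 / √(2 × 0.1275 × (1 − R²) / 874) − 1.96).

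The SAP gives no R², so these values are assumptions:

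| Assumed total R² | Power |
|---|---|
| 0 | 88.5% |
| 0.03 | 89.4% |
| 0.05 | 90.0% |
| 0.08 | 90.9% |
| 0.12 | 92.1% |

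An R² of about 0.049 is enough to return to 90%.

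**Step 4: what the score itself adds.** The planned covariates already account for some of the R², so only the increment counts.

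- Planned set at 0.03, total with score 0.08 to 0.12: 1.5 to 2.7 points of power. In patients, 0.97/0.92 = 1.05 to 0.97/0.88 = 1.10, or about 5% to 10% more.
- Planned set at 0.05, same totals: 0.9 to 2.1 points. In patients, 0.95/0.92 = 1.03 to 0.95/0.88 = 1.08, or about 3% to 8% more.

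**Step 5: check by simulation.** Standardised risk differences were taken from logistic models with 874 per arm, 15% mortality, no centre effect and 4000 runs per scenario. A covariate of assumed strength standing for the planned set cut the variance by about 3%. Adding a second, of assumed moderate to strong extra value, brought the total cut to between 5% and 15%. Under the formula in step 3, that is again a gain of about 1 to 3 points.

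**The case against.** The strongest reply is that the SAP makes no mistake here. It prespecifies a valid model that contains every factor used in randomisation plus age and gender. Nothing in that choice is biased or undefined. This stands, and the point is one of efficiency only.

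Second, the size rests on figures that are not in the SAP. If age, septic shock and centre together explain 5% of the variance instead of 3%, the planned model already has 90% power. This also stands. A reader might infer that the endpoint is underpowered and that the score is needed to rescue it. The documents do not support that: the unadjusted shortfall is 1.5 points, and the planned covariates may close it.

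Third, a reader might infer that the scores are available for every participant and so cost nothing to use. Table 6 provides for missing values of both. Handling missing data also expects gaps in SOFA and fills them from the day before, then the day after. The wording leaves unclear whether this applies to the baseline score. If it does, a post-randomisation value could enter the model. That is a reason to prefer APACHE II and to fix a rule for missing values, but not a reason to leave severity out.

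Fourth, a new covariate helps only the adjusted estimate. If the unadjusted interval must also clear the margin, the decision gains nothing. This is correct, and it is why the fix has to name the deciding estimate.

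**Conclusion.** The point holds as a missed efficiency. The mortality model reuses covariates chosen for another outcome and leaves out graded severity scores that the SAP lists as pre-randomisation measures. The probable gain from one score is roughly 1 to 3 points of power. This assumes 874 evaluable patients per arm, 15% mortality in both arms compared, the 5.4-point margin, and a rise in explained variance from about 3–5% to about 8–12%. The last of these cannot be checked from the SAP. The case for changing rests on the low cost of the change and the weight the SAP gives to this endpoint.

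A covariate would not put right the sample size statement. That 2760 omits the withdrawal allowance for mortality is a separate matter and stays true whichever model is fitted.

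**What to change.** Before unblinding, amend Analysis methods as follows.

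- Add baseline APACHE II as a single continuous covariate to the mixed logistic models for 28-day and 90-day mortality, using only pre-randomisation values. If SOFA is chosen instead, state that the day-after fallback under Handling missing data does not apply to the baseline covariate.
- Replace missing baseline scores with the overall mean, ignoring arm and outcome, so that nobody is dropped from the intention-to-treat analysis.
- Name the adjusted standardised (marginal) risk difference and its 95% confidence interval as the estimate that decides non-inferiority. Keep the currently planned model and the unadjusted estimate as sensitivity analyses. Template Table 22 is laid out for adjusted odds ratios and needs the risk difference added.
- Separately, restate the sample size for mortality: 2760 gives about 88.5% unadjusted power after 5% withdrawal, and 2904 would be needed for 90%.

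The cost is a few lines in the SAP, with no extra patients or data collection. The downside is simple imputation of missing baseline scores, and the gain shrinks as more of them are missing.
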